#### 3. STUDY OVERVIEW

Subjects in this randomized, double-blind, placebo controlled, parallel-group, multiple-center study will be assigned to treatment with the investigational products or placebo control according to a randomization scheme.

- Part I\*: 24 weeks: Subjects will be randomized to Placebo,

  AS012 in 3:3:1:3:1 ratio (approximately first 45% of enrolled subjects) or in 1:1:3:1:3 (approximately remaining 55% enrolled subjects).
  - \*Part I includes week 24 assessments
- Part II: week 24 to week 52: Subjects initially randomized to placebo will be re-randomized to AS012 in 1:1 ratio. Subjects originally randomized to AS012 doses will remain on their assigned dosing regimen until the end of Part II (week 52).
- Part III: week 52 to week 64: After week 52 (or early termination of study treatment prior to week 52), the study treatment will be stopped and all subjects will enter the follow-up period to monitor safety and tolerability for 12 weeks following last dose of study treatment.

May 20, 2022 Protocol: **AS012-20-01** Page 19 of 88

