### Clinical Evaluations will be performed at:

```
Visit 1: Screening Visit (Week ≥ -4 / Day -28 to -1);
Visit 2: Baseline Visit (Week 1 / Day 1);
Visit 3: Interim Visit (Week 4 / Day 29 ± 3 Days);
Visit 4: Interim Visit (Week 12 / Day 85 ± 3 Days);
Visit 5: Interim Visit (Week 16 / Day 113 ± 3 Days);
Visit 6: Interim Visit (Week 20 / Day 141 ± 3 Days);
Visit 7: Interim Visit (Week 24 / Day 169 ± 3 Days);
Visit 8: Interim Visit (Week 28 / Day 197 ± 3 Days);
Visit 9: Interim Visit (Week 36 / Day 253 ± 3 Days);
Visit 10: Interim Visit (Week 44 / Day 309 ± 3 Days);
Visit 11: Interim Visit (Week 48 / Day 337 ± 3 Days);
Visit 12: End of Treatment Visit (Week 52 / Day 365 ± 3 Days);
Visit 13: Follow-up Visit (Week 64 / Day 449 ± 3 Days);
```

Subjects will be admitted into the study after informed consent has been obtained. An Unscheduled Visit is allowed at any time, for any reason, if in the Principal Investigator's opinion it is warranted. If a Subject is discontinued from the study during an Unscheduled Visit, the Unscheduled Visit will be referred to as an Early Discontinuation Visit. For all the subjects who discontinue the study prior to Visit 7 all efforts should be made to conduct a visit at, or close to week 24 to collect focused area assessments. Regardless of the reason, subjects discontinued from IP prior to the end of study will be required to complete the End of Study (EoS) assessment within 2 weeks after the last dose.

[figure not shown]
Randomization and re-randomization will be stratified by stability of disease (stable vs. non-stable)

The assigned Investigational Product will be administered orally three tablets three times a day, in the morning, in the afternoon, and in the evening according to a randomization scheme. Subjects will be required to use diaries to document the date of study treatments, any missed treatments and the occurrence of all adverse events.

[figure not shown]
The duration of each Subject's participation in the study will be approximately 64 weeks (449 days).

If the Principal Investigator determines that the Subject's condition has worsened to the degree that it is unsafe for the Subject to continue in the study (e.g. an increase in VASI score from baseline by  $\geq 25\%$ ), the Subject may be discontinued from the study as a treatment failure and the Subject may be treated using the standard care.

May 20, 2022 Protocol: **AS012-20-01** Page 20 of 88

May 20, 2022 Protocol: **AS012-20-01** Page 21 of 88

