3. STUDY OVERVIEW

3.1 Study Design

Subjects in this randomized, double-blind, placebo controlled, parallel-group, multiple-center study will be assigned to treatment with the investigational products or placebo control according to a randomization scheme.

- Part I: 24 weeks: Subjects will be randomized to Placebo,
 or AS012 in 3:3:1:3:1 ratio (approximately first 45% of enrolled subjects) or in 1:1:3:1:3 (approximately remaining 55% enrolled subjects).
- Part II: week 24 to week 52: Subjects initially randomized to placebo will be rerandomized to AS012 in 1:1 ratio. Subjects originally randomized to AS012 doses will remain on their assigned dosing regimen until the end of Part II (week 52).
- Part III: week 52 to week 64: After week 52 (or early termination of study treatment prior to week 52), the study treatment will be stopped, and all subjects will enter the follow-up period to monitor safety and tolerability for 12 weeks following last dose of study treatment.

Clinical Evaluations will be performed at:

- Visit 1: Screening Visit (Week \geq -4 / Day -28 to -1);
- Visit 2: Baseline Visit (Week 1 / Day 1);
- Visit 3: Interim Visit (Week 4 / Day 29 ± 3 Days);
- Visit 4: Interim Visit (Week 12 / Day 85 ± 3 Days);
- Visit 5: Interim Visit (Week 16 / Day 113 ± 3 Days);
- Visit 6: Interim Visit (Week 20 / Day 141 ± 3 Days);
- Visit 7: Interim Visit (Week 24 / Day 169 ± 3 Days);
- Visit 8: Interim Visit (Week 28 / Day 197 ± 3 Days);
- Visit 9: Interim Visit (Week $36 / \text{Day } 253 \pm 3 \text{ Days}$);
- Visit 10: Interim Visit (Week 44 / Day 309 ± 3 Days);
- Visit 11: Interim Visit (Week 48 / Day 337 \pm 3 Days);
- Visit 12: End of Treatment Visit (Week 52 / Day 365 ± 3 Days);
- Visit 13: Follow-up Visit (Week 64 / Day 449 \pm 3 Days);

Subjects will be admitted into the study after informed consent has been obtained. An Unscheduled Visit is allowed at any time, for any reason, if in the Principal Investigator's opinion it is warranted. If a subject is discontinued from the study during an Unscheduled Visit, the Unscheduled Visit will be referred to as an Early Discontinuation Visit. Subjects discontinued from Investigational Product (IP) prior to the end of study will be required to complete the End of Study (EoS) assessment within 2 weeks after the last dose.

Randomization and re-randomization will be stratified by stability of disease (stable vs. non-stable)

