6.1.1 Treatment Groups

Findings collected up to Week 24 visit will be analyzed by treatment groups based on the treatments that subjects take in Part I of the study:

- Placebo
- AS012
- AS012
- AS012
- AS012

Findings collected after Week 24 visit (including those in the follow-up part of the study) will be analyzed by treatment groups based on the treatments that subjects take in Part II of the study:

- Placebo/AS012
- Placebo/AS012
- AS012
- AS012
- AS012
- AS012

Note that subjects initially randomized to Placebo and re-randomized to AS012 doses after Week 24 will not be pooled with subjects taking the same doses from the study start due to different exposure times.

Adverse events will be analyzed by actual treatment at the time of event onset, i.e., using the same treatment groups as findings collected up to Week 24.

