6.11.1 Adverse Events

Adverse Events will be coded using the MedDRA (Version 23.1) AE coding system for purposes of summarization.

[figure not shown]
An AE will be considered as treatment-emergent (TEAE) if the date of onset is on or after the date of the first study drug administration. AEs with unknown start dates will be counted as treatment-emergent unless the AE resolution date is prior to the study drug start date. If the start date is partially missing, the AE will be considered treatment-emergent, unless the month and year (when available) rule out the possibility that the event occurred post start of study drug dosing.

A TEAE is defined as treatment-related if its relationship to study medication is recorded as "Possible", "Probable" or "Definite" on the eCRF. In case the relatedness was not assessed, the most conservative result (related) will be chosen for the analysis.

For subjects initially randomized to Placebo and later re-randomized to AS012 AEs will be assigned to either Placebo or AS012 treatment based on the date of onset, i.e., AEs that start prior to the first dose of AS012 will be assigned to the Placebo treatment and AEs that start on or after the date of the first AS012 dose will be assigned to the AS012 treatment.

TEAEs will be defined as occurring in Part I of the study if the date of onset is prior to the date of the subject's Week 24 visit. For subjects who discontinue prior to Week 24 visits, all their TEAEs will be defined as occurring in Part I. AEs starting on or after the date of the subject's Week 24 visit will be defined as occurring after Part I.

All summaries of TEAEs will be presented in three ways:

In summaries of TEAEs a subject experiencing the same AE multiple times on the same treatment will only be counted once for that preferred term and treatment. Similarly, if a subject experiences multiple AEs within the same system organ class on the same treatment that subject will be counted only once in that system organ class and treatment. When summarizing AEs by severity, only the most severe occurrence within the preferred term or system organ class and treatment will be used. Similarly, when summarizing AEs by

relationship to study drug, only the most related occurrence within the preferred term or system organ class and treatment will be selected for displays in summary tables.

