An overall summary for the Safety population will include, by treatment and overall, the number and percentage of subjects reporting at least 1 TEAE in the following categories:

- Any TEAE
- Treatment-related TEAE
- Serious TEAE
- Treatment-related serious TEAE
- TEAE leading to discontinuation of the study medication
- Treatment-related TEAE leading to discontinuation of the study medication
- TEAE requiring temporary interruption of study medication
- Treatment-related TEAE requiring temporary interruption of study medication
- TEAE leading to death.

The following TEAE frequency tables will be prepared summarizing the overall number of TEAEs, the number and percentage of subjects reporting at least one TEAE by MedDRA System Organ Class (SOC) and preferred term (PT), by treatment group for the Safety population:

- All TEAEs
- Serious TEAEs
- Treatment-related TEAEs
- AEs leading to discontinuation of the study medication
- TEAEs by Severity
- TEAEs by Relationship to Study Drug.

Overall summary of TEAEs and the summary of TEAEs by SOC and PT will be presented separately for TEAEs occurring in Part I, occurring after Part I and for all TEAEs for subjects initially randomized to AS012 treatment.

All information pertaining to AEs noted during the study will be listed by subject, detailing verbatim, preferred term, system organ class, start date, stop date, intensity, outcome, action taken and causal relationship to the study drug. The AE onset will also be shown relative (in number of days) to the date of first administration of the study drug. In addition the AE duration (if AE Stop Date is available) will be evaluated as below and presented (in number of days).

AE Duration = AE Stop Date - AE Start Date + 1

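### AE summary tables pool 28 weeks on drug with 12 drug-free weeks, and no AE summary described in the SAP isolates the follow-up

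*SAP*

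**What the plan says.** SAP 6.11.1 classes an AE as treatment-emergent when its onset is on or after the first study drug administration. No end is set relative to the last dose. Protocol 10.5 brings AEs up to the follow-up visit into the safety analysis, so Part III events enter the tables.

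SAP 6.11.1 divides time once, at the Week 24 visit: "AEs starting on or after the date of the subject's Week 24 visit will be defined as occurring after Part I". Subjects who discontinue before that visit have all their TEAEs placed in Part I. The overall summary and the summary by system organ class and preferred term "will be presented separately for TEAEs occurring in Part I, occurring after Part I and for all TEAEs for subjects initially randomized to AS012 treatment".

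On attribution, SAP 6.1.1 states: "Adverse events will be analyzed by actual treatment at the time of event onset". It then uses the Part I group list, which is placebo and four AS012 groups. For placebo subjects switched to AS012, SAP 6.11.1 assigns every AE from the first AS012 dose onward to AS012, with no end date.

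Protocol section 3 describes Part III thus: "the study treatment will be stopped and all subjects will enter the follow-up period to monitor safety and tolerability for 12 weeks following last dose". SAP 3.1 says the same.

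**The concern.** After the last dose a subject's actual treatment is none, so the SAP's rule of analysing AEs by actual treatment at onset cannot be applied to Part III with the groups it offers. For switched placebo subjects the attribution of follow-up events to AS012 is explicit. For the four original AS012 arms it follows from the group list and is not stated outright.

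The sponsor runs twelve weeks of follow-up to learn about safety after stopping, but the AE tables described do not report that period on its own. A reader of the after-Part-I table cannot tell whether an event counted under a dose arose during dosing or weeks after it ended. Late on-drug tolerability by dose, which a dose-ranging study should show, is read from a figure that also contains drug-free time.

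**Working it through.** **Inputs.** The visit schedule (Protocol section 3, SAP 3.1) puts the Week 24 visit at Day 169, end of treatment at Day 365 and the follow-up visit at Day 449. The statistics planned in SAP 6.11.1 are the number of TEAEs and the number and percentage of subjects with at least one. Neither document gives an AE rate, so event risks and hazards below are assumptions.

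**Reproducing the stated follow-up length.** 449 − 365 = 84 days; 84 / 7 = 12 weeks. This agrees with the plan.

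**Share of drug-free time for a completer.**
- Part II on drug: 365 − 169 = 196 days (28 weeks).
- After-Part-I window: 449 − 169 = 280 days (40 weeks).
- Off-drug share after Part I: 84 / 280 = 30%.
- Off-drug share of the all-TEAE table for subjects on AS012 from the start: 84 / 448 = 18.75%, where 448 = 449 − 1 elapsed days.

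**Effect on the percentage of subjects.** Let p be the true 28-week on-drug incidence and r the ratio of off-drug to on-drug hazard, each hazard constant within its period. The tabulated 40-week percentage is 1 − (1 − p)^((28 + 12r)/28). With p = 10%:

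| r | exponent | percentage shown |
|---|---|---|
| 0 | 28/28 = 1.000 | 10.0% |
| 0.5 | 34/28 = 1.214 | 12.0% |
| 1 | 40/28 = 1.429 | 14.0% |
| 2 | 52/28 = 1.857 | 17.8% |
| 3 | 64/28 = 2.286 | 21.4% |

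The exponent is also the factor by which the expected number of TEAEs in the window exceeds the on-drug number. At r = 1, 12/40 = 30% of the counted events arise off drug.

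At r = 1, on-drug incidences of 2%, 5%, 20% and 40% are shown as 2.8%, 7.1%, 27.3% and 51.8%, inflation by a factor of 1.42 falling to 1.30.

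**All-TEAE table, r = 1.** 1 − (1 − p)^(64/52): a 52-week on-drug incidence of 10% is shown as 12.2%.

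**Direction.** Extending the window can only add subjects with an event, so the percentage never falls. An event confined to on-drug time (r = 0) keeps its percentage exactly. An event confined to the period after stopping contributes nothing to the on-drug figure but is still displayed under AS012.

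**Part I.** Off-drug events can reach the placebo-controlled comparison only through subjects who stop before Week 24. How long they are observed off drug is unclear. The Part III description gives 12 weeks after last dose. Protocol 7.13 and 7.15 require the end-of-study assessment within 2 weeks of last dose. Protocol 10.5 uses 4 weeks after last dose when the follow-up visit falls outside its window. The effect cannot be sized from the documents and may be small.

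**The case against.** The strongest defence is that the follow-up is visible elsewhere. SAP 6.11.1 lists every AE with start and stop dates and onset day, so for a completer an onset after about Day 365 marks the drug-free period. Vital signs, ECG and physical examination are summarised by visit, and all three are done at Week 64. This stands. A reader might infer from the pooled tables that safety after stopping cannot be seen at all; the documents do not support that. What remains is that the listing counts days from first dose rather than last dose, and a listing is not a summary by dose.

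A reader might also infer that drug-free time dilutes on-drug AE rates, by 30% for a purely on-drug event. That would apply to a rate per unit of time, and the visible SAP plans none. Nor do the documents name withdrawal effects as the purpose of Part III; they speak of safety and tolerability in general.

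The consequence is also limited. There is no concurrent placebo after Week 24, completers in every dose group have the same scheduled follow-up, Protocol 9.7 plans no inferential safety analysis, and including follow-up AEs is a deliberate protocol choice. All of this stands. It argues for keeping the total-events tables, not against showing the two periods separately.

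Finally, the list introduced in SAP 6.11.1 as three ways of presenting TEAEs is missing from the public text, and the table shells are a separate document. An off-treatment display could exist there. But the same section later names three presentations, and none isolates the follow-up.

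**Conclusion.** The point holds for the AE summary tables. The on-treatment window has no end, there is no off-treatment category, and Parts II and III share one table, which conflicts with the SAP's own rule of analysis by actual treatment at onset. The 30% drug-free share follows directly from the visit schedule for a completer. The inflation figures rest on constant hazards, full follow-up to Week 64 and assumed event risks. The direction does not depend on those risks: percentages stay the same or rise, which for an AE table is the conservative side.

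A broad contamination of the placebo-controlled safety comparison is not supported, because only early discontinuers carry off-drug events into Part I. This is a cheap improvement to what the AE tables can show, and it does not threaten the trial's main conclusions.

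**What to change.** In SAP 6.11.1, add a flag derived from the date of last dose plus a carry-over window that the sponsor specifies in advance. Tabulate after-Part-I AEs in two sets: on-treatment, and post-treatment by last treatment taken. Apply the same flag to subjects who stop before Week 24, so that the Part I comparison can be shown for on-treatment events. Keep the existing all-TEAE tables as back-up, so that no event is lost to the choice of window.

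One detail needs care. SAP 6.8 collects the date of last dose on the End of Study eCRF, but replaces a missing one with the date of the last visit. Under the new split, that rule could label off-drug events of subjects lost to follow-up as on-treatment. Those subjects should be identified in the dataset and their number footnoted. The fallback appears in the paragraph on subjects initially randomised to AS012, so the SAP should also say what applies to switched placebo subjects.

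The cost is SAP wording, one derived flag, one extra set of tables and a decision on the carry-over window. No new data are needed.

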6.11.2 Laboratory tests

A central laboratory will be used for all assessments unless noted otherwise. The laboratory assessments include:

Thyroid function: at study Visits 1, 7, and 12 (screening and Weeks 24 and 52) a blood sample will be collected for free T4 and TSH testing.

Hematology: at all study visits a blood sample will be collected for total and differential WBC count, Absolute Neutrophil count (ANC), Absolute Lymphocyte count (ALC), Platelet count, Hemoglobin, Hematocrit.

Lipid profile: at the study Visits 1, 2, 7, and 12 (Screening and study Weeks 1, 24, and 52) a blood sample will be collected for LDL, HDL and total cholesterol and triglycerides testing. The test does not need to be repeated at study Visit 2 if the screening assessment (visit 1) was performed within 2 weeks of Visit 2.

Clinical chemistry: at all study visits a blood sample will be collected for sodium, potassium, chloride, calcium, magnesium, bicarbonate, phosphate, blood urea nitrogen, random glucose, albumin, total protein, alkaline phosphatase, creatinine, Alanine aminotransferase (ALT), AST, gamma glutamyl transferase (GGT), total bilirubin, conjugated bilirubin testing.

Coagulation profile: at the study Visits 1, 2, 7, and 12 (Screening and study Weeks 24, and 52) a blood sample will be collected for PT and INR testing. The test does not need to be repeated at study Visit 2 if the screening assessment (Visit 1) was performed within 2 weeks of Visit 2.

Serology: at Screening visit a blood sample will be collected for: HIV antibodies, HBsAg, and HCV antibodies testing.

Serum pregnancy test: at Screening visit a blood sample will be collected for serum beta-hCG testing.

The following tests will be performed at a clinic site:

Urinalysis dipstick: at the study Visits 1 to 12 (Screening and study Weeks 1 to 52) a urine sample will be collected for pH, specific gravity, protein, glucose, ketones, and blood testing. The test does not need to be repeated at study Visit 2 if the screening assessment (Visit 1) was performed within 2 weeks of Visit 2.

Microscopic exam may be performed at the local or central laboratory at the discretion of the investigator if the dipstick is positive (i.e., trace or above). Only dipstick results will be available in the study database.

Urine Pregnancy Test: at all study visits a urine sample will be collected in women of childbearing potential and the results of all pregnancy tests (positive or negative) will be documented.

A positive result should be confirmed by a different brand of UPT. A confirmed positive urine pregnancy test during the treatment periods of the study requires immediate interruption of study treatment and the subject must be discontinued from the study.

For hematology, chemistry, thyroid function, and coagulation profile the labs that were abnormal and clinically significant at end of treatment (Week 52) are needed at safety follow-up visit (Week 64).

Hematology, chemistry (including lipid profile and thyroid function, and coagulation parameters and their changes from baseline will be summarized descriptively by visit and treatment group. Urinalysis dipstick results will be summarized categorically (positive or negative).

Shifts from baseline among the categories Normal (within the reference range), Low (below the reference range), and High (above the reference range) will be presented by visit.

All results will be listed.

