### 9.7 Safety Assessment

Safety Assessments will include vital signs, physical examination, adverse events (AEs), laboratory tests, ECG monitoring, chest X-ray (if not done in last 6 months) and Columbia-Suicide Severity Rating Scale (C-SSRS).

The safety of AS012 will be evaluated by:

- o Incidence, seriousness and severity of all adverse events
- Shifts from baseline in hematology and laboratory tests
- Change from baseline in ECG parameters; Frequencies and percentages of ECG findings

The extent of exposure will be summarized using descriptive statistics. No inferential analyses are planned.

Incidence of all adverse events reported during the study will be summarized using the Medical Dictionary For Regulatory Activities (MedDRA) dictionary by System Organ Class and Preferred Term, by treatment group, severity, and relationship to study drug.

An AE is considered treatment emergent if it was not present prior to the first dose of treatment or, if it was present, it worsened in severity or treatment attribution.

Safety analyses will be performed on the Safety Population. All safety data will be listed by treatment and subject in data listings. AEs will also be summarized by actual dose at time of onset of the AE to account for possible dose reductions over the course of the study.

May 20, 2022 Protocol: **AS012-20-01** Page 50 of 88

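### SAP 6.11.2 summarises all dipstick results as positive or negative, a rule that does not fit pH and specific gravity and cannot show worsening in subjects already positive at baseline

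*SAP*

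**What the plan says.** SAP 6.11.2 (Laboratory tests) schedules the dipstick at Visits 1 to 12, where "a urine sample will be collected for pH, specific gravity, protein, glucose, ketones, and blood testing". Visit 2 may be skipped if screening was within the previous two weeks. Protocol 5.5 has the same schedule and the same six analytes.

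The planned summary is one sentence, with no exception by analyte: "Urinalysis dipstick results will be summarized categorically (positive or negative").

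Four other statements bear on it:

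- **Meaning of positive.** SAP 6.11.2 lets the investigator order microscopy "if the dipstick is positive (i.e., trace or above"). Protocol 5.5 says the same. Neither document defines the word anywhere else.
- **Microscopy.** SAP 6.11.2 adds: "Only dipstick results will be available in the study database".
- **Shift tables.** The sentence after the dipstick rule plans "Shifts from baseline among the categories Normal (within the reference range), Low (below the reference range), and High (above the reference range"), by visit. It does not say whether urinalysis is included. Protocol 9.7 lists "Shifts from baseline in hematology and laboratory tests" among the safety evaluations.
- **Listings.** SAP 6.11.2 ends: "All results will be listed".

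**The concern.** A positive/negative split fits a test that reports presence or absence. The SAP applies it to a panel that mixes two numeric readings with four graded ones. Read literally, a programmer cannot build the table for pH or specific gravity and has to improvise. For the graded analytes the split keeps the step from negative to positive and discards every step above it.

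What is at stake is the comparison between doses. The study treats for 52 weeks at several doses, and safety analysis is descriptive only (Protocol 9.7). The tables by treatment group are therefore where a dose pattern in urinary protein or blood would be noticed. A pattern made up of worsening among subjects already positive at baseline would not appear there.

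**Working it through.** The plan states no figure to reproduce. The check sets the rule against the analytes and then counts which grade changes a two-category table can show.

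**1. Does the rule fit each analyte?**

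| Analyte (SAP 6.11.2) | Type of result | Positive/negative rule applies? |
|---|---|---|
| pH | numeric | no |
| Specific gravity | numeric | no |
| Protein, glucose, ketones, blood | ordered grades | yes, with loss of grade |

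The rule does not fit 2 of the 6 analytes.

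**2. Which worsenings can the split show?** The documents do not give the grade scale, so the number of grades *k*, including negative, is assumed to be 4, 5 or 6.

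- Possible upward shifts between two visits: k(k − 1)/2.
- If positive means anything above negative, the visible shifts are those that start from negative: k − 1.
- Hidden shifts: k(k − 1)/2 − (k − 1) = (k − 1)(k − 2)/2.

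| Grades (k) | Upward shifts | Visible | Hidden |
|---|---|---|---|
| 4 | 6 | 3 | 3 |
| 5 | 10 | 4 | 6 |
| 6 | 15 | 5 | 10 |

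These are kinds of shift, not numbers of subjects. The documents give nothing from which to estimate how many subjects would have each kind. Trace to the top grade is among the hidden shifts for every *k* shown.

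**3. Would a higher cut-off help?** Suppose positive started one grade above trace, so that two grades (negative and trace) count as negative. The visible shifts are then 2(k − 2).

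- k = 4: 4 visible of 6, so 2 hidden.
- k = 5: 6 visible of 10, so 4 hidden.
- k = 6: 8 visible of 15, so 7 hidden.

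Trace to the top grade would now be visible. Negative to trace, and every worsening above the cut-off, would not. Moving the cut-off changes which shifts are lost but does not remove the loss.

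**4. Would the Normal/Low/High table help?** If it includes urinalysis, it could cover pH and specific gravity through their reference ranges. For a graded analyte whose normal result is negative, trace and the top grade would both be High. It would then hide the same shifts as in step 2.

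**5. Could other planned data fill the gap?** Microscopy is not in the database. The listings show whatever the eCRF holds, subject by subject, but they do not compare treatment groups.

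**The case against.** The strongest reply has five parts.

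- **The cut-off is borrowed.** Trace or above says when microscopy may be ordered. A reader might infer that the SAP has set trace as the cut-off for the table, but it has not. This part stands: what can be said is that positive is undefined for the summary and that this is the only definition available. Step 3 of the working shows that another cut-off would still lose some worsening.
- **pH and specific gravity may be covered elsewhere.** The shift sentence follows the dipstick rule directly and does not exclude urinalysis. The separate table shells (SAP 9), which are not available here, may also settle the layout. A reader might infer that the plan has no way at all to summarise these two analytes. The documents do not support that; they leave it open.
- **Nothing is lost from the data.** All results are listed. A reader might infer that worsening is concealed outright, but the loss is only in the summary tables. This part stands and limits the point.
- **Urinary safety does not rest on the dipstick alone.** Protocol 5.7 counts an abnormal laboratory finding as an adverse event, and SAP 6.11.1 tabulates treatment-emergent events by severity. Creatinine, blood urea nitrogen and albumin are measured at the study visits and summarised with change from baseline. This lowers the stakes but does not make the dipstick table informative.
- **It is a reporting preference.** For the four graded analytes there is some truth in this. For pH and specific gravity there is not, because the stated rule cannot be carried out.

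**Conclusion.** The point holds for the descriptive summary tables. The rule does not fit 2 of 6 analytes, and the SAP does not say whether the shift table covers them. For the other four, a two-category summary cannot show worsening in a subject already positive at baseline. If positive means trace or above, trace to the top grade appears as no change.

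The count of hidden shifts (3 of 6, 6 of 10 or 10 of 15) rests on an assumed scale of four, five or six grades and on that definition. The qualitative conclusion needs only that the scale has more than one grade above the cut-off.

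A reader might also infer that counting trace results as positive blurs differences between doses. The documents give no frequency of trace results, so no such effect can be shown or sized, and it forms no part of this conclusion. The primary analysis, the sample size and the type I error rate are unaffected. The severity is minor.

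**What to change.** In SAP 6.11.2, replace the dipstick sentence with three statements:

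1. pH and specific gravity are summarised as continuous values with change from baseline, by visit and treatment group, as for the other laboratory parameters. State also whether the Normal/Low/High shift table includes them.
2. Positive is defined for the summary table, separately from the microscopy trigger.
3. Where the database holds the recorded grade, protein, glucose, ketones and blood are also shown as a shift from baseline to worst post-baseline grade, by treatment group. Take the worst grade separately up to Week 24 and after it, in line with the treatment groups in SAP 6.1.1. Otherwise a placebo subject's worst grade could come from the AS012 period. State whether unscheduled results count, since SAP 6.1 keeps them out of by-visit summaries.

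The cost is a short SAP edit, changed shells and one or two more safety tables. Statement 3 depends on the eCRF recording grades, so check that first. If the eCRF holds only positive or negative, the grade table would need a change in data collection, and the sponsor would have to judge whether that is worthwhile for a descriptive table. Statements 1 and 2 do not depend on how grades are recorded, although statement 1 needs the pH and specific gravity readings to be held as numbers.
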